#### ClinicalTrials.gov ID: NCT03390166

### **Study Identification**

Unique Protocol ID:	Tri Fluvac Vaccine phase 2/3
Brief Title:	Immunogenicity and Safety of Tri Fluvac, a Seasonal Trivalent Inactivated Influenza Vaccine in Healthy Thai Adults
Official Title:	A Phase II/III Double Blinded, Randomized, Controlled, Non-inferiority Trial to Evaluate the Immunogenicity and Safety of Tri Fluvac, a Seasonal Trivalent Inactivated Split Virion Influenza Vaccine, in Healthy Thai Subjects Aged 18-49 Years
Secondary IDs:	

#### **Study Status**

Record Verification:	March 2019
Overall Status:	Completed
Study Start:	July 24, 2017 [Actual]
Primary Completion:	March 31, 2018 [Actual]
Study Completion:	February 12, 2019 [Actual]

# **Study Description**

Brief Summary:	The study is aim to evaluate the immunogenicity and safety with two groups of participants who will received a seasonal trivalent split, inactivated influenza vaccine (A/H1N1; A/H3N2 and B) or an active comparator (licensed influenza vaccine
Detailed Description:	This is a phase II/III, non-inferiority double-blinded, randomized, controlled trial of immunogenicity and safety with two groups of participants who will received a seasonal trivalent split, inactivated influenza vaccine (A/H1N1; A/H3N2 and B) or an active comparator (licensed influenza vaccine).
	A total of about 945 healthy Thai male and female adult volunteers 18 through 49 years of age; 630 participants will be randomized to receive the GPO Tri Fluvac and 315 will receive an active comparator (a 2:1 ratio) (inclusion of ~7% lost to follow-up).
	Safety will be assessed for all participants through Day 90 after vaccination. Immunogenicity will be assessed in serum samples obtained at baseline and 21 days after vaccination in a subset of at least 586 individuals randomized to study vaccine and 293 active comparator vaccine recipients.

### Conditions

Conditions:	Influenza
Keywords:	GPO Tri Fluvac Vaccine Tri Fluvac vaccine

# **Study Design**

Study Type:	Interventional
Primary Purpose:	Prevention
Study Phase:	Phase 2/Phase 3
Interventional Study Model:	Parallel Assignment non-inferiority double-blinded, randomized, controlled trial
Number of Arms:	2
Number of Arms: Masking:	2 Double (Participant, Investigator) double blinded
Number of Arms: Masking: Allocation:	2 Double (Participant, Investigator) double blinded Randomized

#### Arms and Interventions

Arms	Assigned Interventions
Active Comparator: GPO Tri Fluvac vaccine	Biological/Vaccine: GPO Tri Fluvac vaccine
630 volunteers will receive a single dose of the seasonal trivalent inactivated influenza vaccine (consisting of A/Michigan/45/2015 (H1N1)pdm-09- like virus, A/Hong Kong/4801/2014 (H3N2)-like virus, and B/Brisbane/60/2008-like virus) produced by GPO Thailand. To be administered via the intramuscular route; the preferred injection site will be the deltoid of the non-dominant arm.	The vaccine will be administered via the intramuscular route; the preferred injection site will be the deltoid of the non-dominant arm.
Active Comparator: Licensed Influenza vaccine 315 volunteers will receive acLicensed Influenza vaccine (seasonal trivalent inactivated split virion influenza vaccine recommended for Southern Hemisphere in 2017 (consisting of A/ Michigan/45/2015 (H1N1)pdm-09-like virus, A/ Hong Kong/4801/2014 (H3N2)-like virus, and B/ Brisbane/60/2008-like virus) 0.5 mL administered intramuscularly (IM) in the deltoid muscle of the non- dominant arm.	Biological/Vaccine: Licensed influenza vaccine The comparator licensed influenza vaccine will be administered via the intramuscular route; the preferred injection site will be the deltoid of the non-dominant arm.

#### **Outcome Measures**

Primary Outcome Measure:

1. Primary Immunogenicity Endpoint: Immune responses to the GPO Tri Fluvac and active comparator vaccine at 21 days post-injection.

null [Time Frame: 21 days post-injection]

2. Primary Safety Endpoints: Number of subjects with all Adverse Events during the study period and % of subjects with

all Adverse Events during the study period null [Time Frame: upto 90 days]

# Eligibility

Minimum Age: 18 Years

Maximum Age: 49 Years

Sex: All

#### Gender Based:

Accepts Healthy Volunteers: Yes

Criteria: Inclusion Criteria:

- Age 18-49 years old on the day of screening, having Thai ID card or equivalent
- Able to read and write in Thai and sign written informed consent form
- Able to attend all scheduled visits and to comply with all trial procedures.
- Healthy or medically stable, as established by medical history and physical examination. For individuals with medical conditions, symptoms/signs, if present must be stable, under control or unchanged for the past three months. If medication is used to treat the condition, the medication dose must have been stable for at least one month preceding vaccination.
- For female participants:

· Not breast feeding, non-pregnant (based on negative urine pregnancy test) and no plan to become pregnant up to Day 60. Women who are not surgically sterile (hysterectomy or tubal ligation) or post-menopausal for more than one year must be willing to use effective contraceptive method to prevent pregnancy until Day 60 after vaccination. Effective methods include intrauterine device, hormonal contraceptives (oral, injectable, patch, implant, ring) or double barrier contraceptives (condom or diaphragm with spermicide). Women with credible history of abstinence may be enrolled at the discretion of the investigator **Exclusion Criteria:**  Participation in another clinical trial involving any therapy within the previous three months or planned enrollment in such a trial during the period of this study. · Hypersensitivity after previous administration of any vaccine. Having a history of H1N1, H3N2 or Flu B infection within 3 months preceding enrollment to the trial Vaccination against influenza in the past 6 months preceding enrollment to the trial · Receipt of any non-study vaccine within four weeks prior to enrollment or refusal to postpone receipt of such vaccines until after the Day 21 visit. History of bronchial asthma, chronic lung diseases, chronic rhinitis History of immunodeficiency state • History of immunosuppression < 6 months prior to immunization · History of anaphylactic or other allergic reactions to influenza vaccine or any vaccine component or excipient (e.g. gentamicin or thimerosal) · History of Guillain-Barré Syndrome. Having acute infection with fever > 38 degree Celsius or noninfectious diseases (within 72 hours) preceding enrollment in the trial · Volunteers who have been taking immunoglobulin products or have had a blood transfusion during past 3 months before the beginning of the trial or planned receipt of such products prior to the Day 21 visit. Current alcohol abuse or drug addiction that might interfere with the ability to comply with trial procedures · Any condition that in the opinion of the investigator would pose a health risk to the subject if enrolled, or could interfere with the evaluation of the

## LIST OF ABBREVIATIONS

AE	Adverse Event
CI	Confidence Interval
cm	Centimeter
CPMP	Committee for Proprietary Medicinal Products
CRF	Case Report Form
CRO	Contract Research Organization
CSR	Clinical Study Report
°C	Degrees Celsius
D	Day
EDC	Electronic Data Capture
EMA	European Medicine Agency
GCP	Good Clinical Practice
GMFR	Geometric Mean Fold Rises
GMT	Geometric Mean Titer
GPO	The Government Pharmaceutical Organization
HA	Hemagglutinin
HI	Hemagglutination Inhibition assay
hCG	Human Chorionic Gonadotropin
ICF	Informed Consent Form
ICH	International Conference on Harmonization
IEC	Independent Ethics Committee
IM	Intramuscular
IRB	Institutional Review Board
IWRS	Interactive Web Response System
LAIV	Live Attenuated Influenza Vaccine
LEC	Local Ethics Committee
LLN	Lower Limit of Normal
mcg	Microgram
mL	Milliliter
N	Number (typically refers to number of participants)
NIBSC	2-UK National Institute for Biological Standards a
NRA	National Regulatory Authorities

ΡI Principal Investigator ds and Control Control Kingdom PPROVED  $\diamond$ ETHICS COMMITTEE e FACULTY OF TROPICAL MEDICINE MAHIDOL UNIVERSITY

ตยาลัยม

- PBS Phosphate buffered saline
- SMT Safety Medical Team
- SAE Serious Adverse Event
- SAP Statistical Analysis Plan
- SOP Standard Operating Procedure
- TIV Trivalent Inactivated Influenza Vaccine
- ULN Upper Limit of Normal
- WHO World Health Organization

APPROVED ETHICS COMMITTEE FACULTY OF TROPICAL MEDICINE MAHIDOL UNIVERSITY

# **1. PROTOCOL SUMMARY**

Title:	A Phase II/III Double Blinded, Randomized, Controlled, Non-inferiority trial to evaluate the Immunogenicity and Safety of Tri Fluvac, a Seasonal Trivalent Inactivated Split Virion Influenza Vaccine, in Healthy Thai Subjects Aged 18 – 49 Years.						
Protocol #:	GPO Tri Fluvac Vaccine Phase II/III						
Description of Study Design:	This is a phase II/III, non-inferiority double-blinded, randomized, controlled trial of immunogenicity and safety with two groups of participants who will received a seasonal trivalent split, inactivated influenza vaccine (A/H1N1; A/H3N2 and B) or an active comparator (licensed influenza vaccine).						
	A total of about 945 healthy Thai male and female adult volunteers 18 through 49 years of age; 630 participants will be randomized to receive the GPO Tri Fluvac and 315 will receive an active comparator (a 2:1 ratio) (inclusion of ~7% lost to follow-up).						
	Safety will be assessed for all participants through Day 90 after vaccination. Immunogenicity will be assessed in serum samples obtained at baseline and 21 days after vaccination in a subset of at least 586 individuals randomized to study vaccine and 293 active comparator vaccine recipients.						
Study Hypothesis:	Immunogenicity: A single dose of the GPO seasonal trivalent split, inactivated influenza vaccine will induce immune responses measured by HI assay to each of the three vaccine antigens and will be non-inferior to active licensed comparator vaccine.						
	Safety : A single dose of the GPO seasonal trivalent split, inactivated influenza vaccine will be safe and well tolerated in adults 18 to 49 years of age.						
Study	Primary objective						
Objectives.	Immunogenicity:						
	To evaluate the immunological non-inferiority seroconversion rate (using HI assay) and Geometric Mean Titre (GMT) of the GPO seasonal trivalent split, inactivated influenza vaccine compared to active comparator vaccine for each of the three vaccine antigens, three weeks after immunization (Day 21) and at the end of follow-up period (Day 90).						
	Safety:						
	To evaluate the safety profile of a single intramuscular dose of the GPO seasonal trivalent split, inactivated influenza vaccine in adults 18 to 49 years of age.						
	To compare the solicited symptoms, AE and SAE between subjects who will receive GPO trivalent split, inactivated influenza vaccine and those who will receive active comparator vaccine.						
	Secondary objective APPROVE	E D					
	To evaluate the HI responses at 3 weeks after immunization in participants with OM MIT without pre-existing HI antibody.	TEE					
	MAHIDOL UNIVER	SITY					

Study Endpoints	Primary Immunogenicity Endpoint:
and Statistical Analysis:	Immune responses to the GPO Tri Fluvac and active comparator vaccine at 21 days post-injection will be analyzed by the following:
	- Number and percentage of participants with seroconversion against each of the three vaccine antigens. Seroconversion is defined as a serum HI antibody titer meeting the following four fold rising criteria:
	
 
Pre-vaccination titer <1:10 and a post-vaccination titer measured on Day 21 of ≥1:40; or
 

	
 
Pre-vaccination titer ≥1:10 and at least a four-fold increase in post-vaccination measured on Day 21.
 

	- Geometric mean titers (GMTs) of serum HI antibodies pre- (Day 0) and post-vaccination (Day 21) for each of the three vaccine antigens.
	Note that titers below the lowest limit of quantitation (i.e., below the starting dilution of assay reported as "< 10") will be set to half that limit (i.e., $10/2 = 5$ ). If a titer is reported as greater or equal to the upper limit of the assay, it will be set to that limit.
	The analyses will be performed on the Total Vaccinated cohort (ITT) and According to Protocol (ATP) cohort for immunogenicity. The primary immunogenicity analysis will be based on the ATP cohort.
	- The Total Vaccinated cohort will include all subjects with a documented vaccine administration.
	- The ATP cohort for immunogenicity will include all evaluable subjects (i.e. those meeting all eligibility criteria, complying with the procedures and intervals defined in the protocol, with no elimination criteria during the study) for whom data concerning immunogenicity outcome variables were available for antibodies against at least one study vaccine antigen component after vaccination.
	Primary Safety Endpoints:
	Number and percentage of subjects with solicited local and systemic reactions during the three days post-injection. In addition, all adverse events (AE) and serious adverse events (SAEs), and new onset of chronic diseases (NOCDs) will be collected for the entire study period. Specifically, the following safety parameters will be monitored and analyzed in terms of the number and proportion of participants reporting the following events will be assessed:
	
 
Solicited local adverse events, including redness/erythema, swelling/induration, pain and limitation of arm movement within 30 minutes of vaccination and over the 3-day period post vaccination (Day 0-3).
 
Solicited systemic adverse events, including fever fatigue/malaise muscle VEC aches, joint aches, chills, nausea and headache within 30 minutes of vaccination and over the 3-day period post vaccination (Day 0-3).
 
Unsolicited adverse events (AEs) occurring within 30 days post vaccination ROPICAL MEDICIN
 

• Serious Adverse Events (SAE) occurring during the entire study period (Days 0-90).

Occurrences of all events will be reported and summarized according to event severity, as "any local AE", or "any systemic AE", and by relationship to administration of study product, as deemed by a blinded study clinician. Percentage of participants experiencing each reaction or event, or at least one reaction or event will be calculated along with two-sided exact 95% CIs. The percentage of participants with solicited AE and SAEs will be compared between vaccine and comparator groups and a two-sided p-value of 0.05 will be considered statistically significant.

Inferential analyses

GMT ratios (GMT active comparator vaccine/GMT GPO Tri Fluvac) and difference of seroconversion rate (with two-sided 95% CI) related to the comparisons of interest will be computed. Acceptance value of GMT ratios at  $\leq 1.5$  and/or difference of seroconversion rate at  $\leq 10\%$  for the upper bound of the 95% CI will be considered for non-inferiority.

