# Secondary Immunogenicity Endpoints and analysis:

The secondary immunogenicity endpoints will be analyzed by the following:

- Number and percentage of participants with a HI antibody titer ≥1:40 (seroprotective level) to each of the three vaccine antigens measured on Day 21 and Day 90.
- Number and percentage of participants who develop at least a four-fold increase in HI antibody titers to each of the vaccine antigen post-vaccination measured on Day 21 and Day 90 segregated by pre-vaccination HI antibody titers (<1:10 or ≥1:10).
- Geometric mean fold rises (GMFRs) of serum HI antibodies (post-vaccination/pre-vaccination) for each of the three vaccine antigens.
- GMTs of serum HI antibodies pre- (Day 0) and post-vaccination (Day 21 and Day 90) for each of the three vaccine antigens segregated by pre-vaccination HI antibody titers (<1:10 or ≥1:10).
- GMFRs of serum HI antibodies (post-vaccination/pre-vaccination) for each of the three vaccine antigens segregated by pre-vaccination HI antibody titers (<1:10 or ≥1:10).

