# **Primary objective**

**Primary Immunogenicity**: To evaluate the immunological non-inferiority seroconversion rate and Geometric Mean Titre (GMT) of the GPO seasonal trivalent split, inactivated influenza vaccine compared to active comparator vaccine for each of the three vaccine antigens at three weeks after immunization (Day 21).

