## **STUDY ENDPOINTS:**

### **Primary endpoint**

## Primary Immunogenicity Endpoints and analysis:

- Number and percentage of participants with seroconversion against each of the three vaccine antigens. Seroconversion is defined as a serum HI antibody titer meeting the following criteria:
  - Pre-vaccination titer <1:10 and a post-vaccination titer measured on Day 21 of ≥1:40; or
  - Pre-vaccination titer  $\geq 1:10$  and at least a four-fold increase in post-vaccination measured on Day 21.
- Geometric mean titers (GMTs) of serum HI antibodies pre- (Day 0) and post-vaccination (Day 21) for each of the three vaccine antigens.

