Appendix 06: Listing of Adverse Event	. 78
Appendix 07: Listing of Illness like Influenza (ILI)	. 78
Appendix 08: Listing of Concomitant Medication	. 79
Appendix 09: List of HAI Assay (Flu A H1 Antigen)	. 80
Appendix 10: List of HAI Assay (Flu A H3 Antigen)	. 80

Study Synopsis

Title: A Phase II/III Double Blinded, Randomized, Controlled, Non-inferiority trial to evaluate the Immunogenicity and Safety of Tri Fluvac, a Seasonal Trivalent Inactivated split virion Influenza vaccine, in healthy Thai subjects aged 18 – 49 years.

Protocol #: GPO Tri Fluvac Vaccine Phase II/III

Description of Study Design:

This is a phase II/III, non-inferiority double-blinded, randomized, controlled trial of immunogenicity, safety and preliminary efficacy with two groups of participants who will received a seasonal trivalent split, inactivated influenza vaccine (A/H1N1; A/H3N2 and B) or an active comparator (licensed influenza vaccine).

A total of about 945 healthy Thai male and female adult volunteers 18 through 49 years of age; 630 participants will be randomized to receive vaccine and 315 will receive an active comparator (a 2:1 ratio) (inclusion of \sim 7% lost to follow-up).

Safety will be assessed for all participants through Day 90 after vaccination. Immunogenicity will be assessed in serum samples obtained at baseline and 21 days after vaccination in a subset of at least 630 individuals randomized to study vaccine and 315 active comparator vaccine recipients.

Study Hypothesis:

Immunogenicity: A single dose of the GPO seasonal trivalent split, inactivated influenza vaccine will induce immune responses measured by HI assay to each of the three vaccine antigens and will be non-inferior to active licensed comparator vaccine.

Safety: A single dose of the GPO seasonal trivalent split, inactivated influenza vaccine will be safe and well tolerated in adults 18 to 49 years of age.

Study Objectives:

Primary objective

Immunogenicity:

To evaluate the immunological non-inferiority seroconversion rate (using HI assay) and Geometric Mean Titre (GMT) of the GPO seasonal trivalent split, inactivated influenza vaccine compared to active comparator vaccine for each of the three vaccine antigens, three weeks after immunization (Day 21) and at the end of follow up period (Day 90).

Safety:

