^d Geometric Mean Fold Rises (GMFR) is the geometric mean of the ratios of post - vaccination to the pre-vaccination (Day 0)

- Seroconversion rate, seroprotection rate and GMTs will be compared between Tri Fluvac and comparator group.

Measure	Study Croup	HAI Assay			
	Study Group	Flu A H1 antibody titer	Flu A H3 antibody titer	Flu B antibody titer	
Day 0					
GMT ^c	Tri Fluvac (N=)	XX.XX (XX.XX, XX.XX)	XX.XX (XX.XX, XX.XX)	XX.XX (XX.XX, XX.XX)	
	Comparator (N=)	XX.XX (XX.XX, XX.XX)	XX.XX (XX.XX, XX.XX)	XX.XX (XX.XX, XX.XX)	
Day 21					
Seroconversion Rate ^a	Tri Fluvac (N=)	XX.XX% (XX.XX%, XX.XX%)	xx.xx% (xx.xx%, xx.xx%)	xx.xx% (xx.xx%, xx.xx%)	
	Comparator (N=)	xx.xx% (xx.xx%, xx.xx%)	XX.XX% (XX.XX%, XX.XX%)	XX.XX% (XX.XX%, XX.XX%)	
Difference in Seroconversion Rate ^b		XX.XX% (XX.XX%, XX.XX%)	XX.XX% (XX.XX%, XX.XX%)	XX.XX% (XX.XX%, XX.XX%)	
GMT ^c	Tri Fluvac (N=)	XX.XX (XX.XX, XX.XX)	XX.XX (XX.XX, XX.XX)	xx.xx (xx.xx, xx.xx)	
	Comparator (N=)	xx.xx (xx.xx, xx.xx)	XX.XX (XX.XX, XX.XX)	xx.xx (xx.xx, xx.xx)	
GMT Ratio ^d		xx.xx (xx.xx, xx.xx)	XX.XX (XX.XX, XX.XX)	xx.xx (xx.xx, xx.xx)	
Day 90					
Seroconversion Rate ^a	Tri Fluvac (N=)				
	Comparator (N=)				
Difference in Seroconversion Rate ^b					
GMT ^c	Tri Fluvac (N=)				
	Comparator (N=)				

TREF 02: Summary of Non-inferiority Established Based on Seroconversion Rate Differences and GMT Ratios

GMT Ratio^d

Note: a Sero-conversion is defined as 4 fold rising titer from baseline (Day 0). Values are the percent of subjects in each group (with 95% CI).

^b Percent difference in Seroconversion rate (with 95% CI). Clinical margin ≤ 10 %

^c Values are the geometric means titer (GMT) (with 95% CI) for the subjects in each group.

^d Values are the geometric means of the individual at Day 21 and Day 90 of Active comparator vaccine/ GPO Tri Fluvac HAI ratio. Clinical margin ≤ 1.5

- Non-inferiority criteria based on GMT ratio if the ratio for each HI assay at ≤ 1.5 and / or difference of seroconversion rate at $\leq 10\%$ for the upper bound of the 95% CI.

Day	Antibody Titer	GMT Ratio [Comparator/ Tri Fluvac] (95% CI)	Non- inferiority (Upper bound of the two-sided 95% CI of GMT ratio ≤ 1.5)
Day 21	Flu A H1	x.xx (x.xx - x.xx)	Yes / No
	Flu A H3		
	Flu B		
Day 90	Flu A H1		
	Flu A H3		
	Flu B		

TREF 03: Summary Immunogenicity Result: GMT Ratio

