Note: Non-inferiority criteria based on GMT ratio if the ratio for each HI assay at ≤ 1.5 and / or difference of sero-conversion rate at $\leq 10\%$ for the upper bound of the 95% CI.

TREF 04: Summary Immunogenicity Result: Sero-conversion Rate (SCR) Difference

Day	Antibody Titer	SCR (%) difference [Comparator-Tri Fluvac] (95% CI)	Non- inferiority (Upper bound of the two-sided 95% CI of SCR Difference ≤ 10%)
Day 21	Flu A H1	x.xx (x.xx - x.xx)	Yes / No
	Flu A H3		
	Flu B		
Day 90	Flu A H1		
	Flu A H3		
	Flu B		

Note: Non-inferiority criteria based on GMT ratio if the ratio for each HI assay at ≤ 1.5 and / or difference of seroconversion rate at $\leq 10\%$ for the upper bound of the 95% CI.

FREF 09: Summary Geometric Mean Titer (GMT) with 95% CI Against Each of Three Vaccine Antigens at Day 21

FREF 10: Summary Geometric Mean Titer (GMT) with 95% CI Against Each of Three Vaccine Antigens at Day 90

FREF 11: Summary Percentage of Seroprotection with 95% CI Against Each of Three Vaccine Antigens at Day 21

FREF 12: Summary Percentage of Seroprotection with 95% CI Against Each of Three Vaccine Antigens at Day 90

FREF 13: Summary Percentage of Seroconversion with 95% CI Against Each of Three Vaccine Antigens at Day 21

FREF 14: Summary Percentage of Seroconversion with 95% CI Against Each of Three Vaccine Antigens at Day 90

FREF 15: Summary Non-Inferiority Trial of GMTs Ratio and 95% Confidence Interval at Day 21

Note: - Non-inferiority criteria based on GMT ratio if the ratio for each HI assay at ≤ 1.5 and / or difference of seroconversion rate at $\leq 10\%$ for the upper bound of the 95% CI.

FREF 16: Summary Non-Inferiority Trial of GMTs Ratio and 95% Confidence Interval at Day 90

Note: - Non-inferiority criteria based on GMT ratio if the ratio for each HI assay at ≤ 1.5 and / or difference of seroconversion rate at $\leq 10\%$ for the upper bound of the 95% CI.

FREF 17: Summary Non-Inferiority Trial of Seroconversion Difference (%) and 95% Confidence Interval at Day 21

Note: - Non-inferiority criteria based on GMT ratio if the ratio for each HI assay at \leq 1.5 and / or difference of seroconversion rate at \leq 10% for the upper bound of the 95% CI.

FREF 18: Summary Non-Inferiority Trial of Seroconversion Difference (%) and 95% Confidence Interval at Day 90

Note: - Non-inferiority criteria based on GMT ratio if the ratio for each HI assay at ≤ 1.5 and / or difference of seroconversion rate at $\leq 10\%$ for the upper bound of the 95% CI.

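### Day 90 non-inferiority is in the primary objective of the synopsis and SAP but in no primary endpoint, and no rule says how it enters the conclusion

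*Protocol*

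**What the plan says.** **Objective.** Protocol section 1 places primary non-inferiority, for seroconversion and GMT, at "three weeks after immunization (Day 21) and at the end of follow-up period (Day 90"). The SAP synopsis agrees: "three weeks after immunization (Day 21) and at the end of follow up period (Day 90"). Protocol section 3 has only "for each of the three vaccine antigens at three weeks after immunization (Day 21").

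**Endpoint.** The Protocol Summary introduces its primary immunogenicity endpoint with "Immune responses to the GPO Tri Fluvac and active comparator vaccine at 21 days post-injection will be analyzed by the following". Sections 3, 11.3 and 11.5 and the SAP synopsis also keep the primary endpoint at Day 21. The secondary lists in sections 1, 3, 11.3 and 11.5 contain Day 90 measures, for example a four-fold rise "post-vaccination measured on Day 21 and Day 90 segregated by pre-vaccination HI antibody titers".

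**Tables and figures.** TREF 03 (GMT ratio, limit 1.5) and TREF 04 (seroconversion difference, limit 10%) have a Yes/No non-inferiority column and list all three antigens at Day 21 and again at Day 90. TREF 02, which summarises the non-inferiority findings, has Day 90 rows. FREF 16 shows the Day 90 GMT ratio, and the title of the companion figure is "FREF 18: Summary Non-Inferiority Trial of Seroconversion Difference (%) and 95% Confidence Interval at Day 90".

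**Definition.** The first limb of the protocol's seroconversion definition is "Pre-vaccination titer <1:10 and a post-vaccination titer measured on Day 21 of ≥1:40; or". The second is a four-fold rise from a baseline of at least 1:10, again at Day 21. The footnote to TREF 01 and TREF 02, both of which have Day 90 rows, reads "Sero-conversion is defined as 4 fold rising titer from baseline (Day 0").

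**Sample size.** Protocol sections 1 and 11.2 list Day 21 rates and standard deviations only. H3 seroconversion drives the total.

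**The concern.** A primary objective should map onto a primary endpoint, a sample size and a decision rule. Day 21 has all three, apart from the unresolved and/or between the two measures. Day 90 has a place in the objective in two of three statements and has limits in the SAP tables. It has no primary endpoint and no part in the sample size, and nothing says what its result does to the conclusion.

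A pass at Day 21 with a fail at Day 90, or the reverse, therefore has no pre-specified reading. One reader could report success on section 3 while another reports failure on the SAP objective, each citing an approved text. Section 11.3 makes no multiplicity adjustment, so no error control is in place that would cover a choice between visits.

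**Working it through.** **1. The plan's own figure.** Inputs from Protocol sections 1 and 11.2: H3 seroconversion 0.535 in both arms, margin 0.10, one-sided alpha 0.025, power 0.80, allocation 2:1.

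- Comparator n = (1.960 + 0.842)² × 0.535 × 0.465 × (1 + 1/2) / 0.10² = 293 after rounding up.
- Vaccine n = 586, so 879 evaluable. This matches the plan, which then allows 7% for exclusion from the ATP cohort and reaches 945.
- Power at 293:586: SE = √(0.535 × 0.465 × 1.5 / 293) = 0.0357, and Φ(0.10/0.0357 − 1.960) = Φ(0.842) = 80.0%.

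The calculation is sound, and it is a Day 21 calculation.

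**2. Day 90 alone.** The documents give no Day 90 seroconversion rate, so a range is assumed, with true difference zero and 293:586 evaluable. Power = Φ(0.10/√(p(1−p) × 1.5/293) − 1.960).

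| Assumed Day 90 rate | Power |
|---|---|
| 0.5 | 79.8% |
| 0.4 or 0.6 | 81.4% |
| 0.3 or 0.7 | 86.2% |
| 0.2 or 0.8 | 93.7% |

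The worst case, a rate of 0.5, would need 885 evaluable against 879. Greater loss by Day 90 would matter somewhat. At a rate of 0.535 with 2:1 kept, 90% of the 315 comparators evaluable gives 78.7%, and 85% gives 76.4%.

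**3. If both visits had to pass (H3 seroconversion, illustration).** Assume 80% power at each visit and a correlation ρ between the two test statistics, which the documents do not give. Joint power is the bivariate normal probability Φ₂(0.842, 0.842; ρ).

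**4. If either visit sufficed (illustration).** One-sided error per strain and endpoint = 1 − Φ₂(1.960, 1.960; ρ). At ρ = 0 this is 1 − 0.975² = 4.9%.

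| ρ | Power, both required | Error, either suffices |
|---|---|---|
| 0 | 64.0% | 4.9% |
| 0.5 | 68.7% | 4.5% |
| 0.8 | 72.9% | 3.9% |
| 0.9 | 75.0% | 3.5% |

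Day 21 alone has 80.0% power and 2.5% error.

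**5. The two definitions.** Protocol section 11.5 sets a titre below 10 to 5. Take a subject who goes from below 10 to 20. The ratio is 20/5 = 4, so the SAP footnote, read literally, counts a seroconversion. The protocol requires at least 1:40 from such a baseline, so it does not.

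**The case against.** The strongest reply is that the operative text already settles the matter. Every primary endpoint statement is at Day 21, as is the registry outcome reproduced in both documents. Section 11.3 ties the non-inferiority conclusion to the primary endpoint in the ATP cohort. The SAP's Day 90 rows are not labelled primary. On this reading the Day 90 clause is a stray phrase in the objective. That is probably what was intended, and it supports the direction of the fix. It does not remove the contradiction, because two statements of the primary objective say otherwise and the SAP tables act on them.

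Some stronger readings are tempting but unsupported:

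- **That Day 90 has no seroconversion definition or criterion.** The SAP footnote covers the Day 90 rows, and TREF 03 and TREF 04 state a limit for each row. Only the step from those rows to the overall conclusion is missing.
- **That six more primary verdicts exist** (three antigens × two measures). The Day 90 cells exist, but no endpoint statement makes them primary.
- **That the trial is underpowered or its error inflated.** No text requires both visits to pass, beyond the word joining them in the objective, and none allows either to suffice. The 64% and 4.9% are the zero-correlation extremes. Zero correlation is unlikely for repeated titres in the same people that share a baseline.

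On the definition, both synopses call the two-part rule a four-fold criterion, so the footnote may be shorthand. That is possible, but a programmer working from the table shell would not see the 1:40 condition.

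**Conclusion.** The inconsistency stands and should be corrected. Day 90 is in the primary objective in the Protocol Summary and the SAP, but not in section 3 or any primary endpoint. The SAP judges it at the Day 21 limits, and nothing says what follows from the result.

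No fixed loss of power or error inflation can be assigned. The both-visits range (64–75% for H3 seroconversion) and the either-visit range (3.5–4.9%) rest on rules and correlations that the documents do not state. They show only why the role of Day 90 must be written down. The missing Day 90 sample size matters little by itself, since power is about 80% or more if the true difference is zero and as many subjects are evaluable as at Day 21.

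The definition mismatch is a smaller, separate defect. It affects subjects with baseline below 1:10 who rise at least four-fold without reaching 1:40, if the footnote is applied as written.

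**What to change.** 1. In the Protocol Summary and the SAP synopsis, make Day 21 the sole time point of the primary immunogenicity objective, as section 3 already does.
2. List the Day 90 GMT ratio and seroconversion difference as secondary, reported with 95% confidence intervals, and state that they do not enter the non-inferiority conclusion.
3. Carry that label through TREF 02, TREF 03, TREF 04, FREF 16 and FREF 18. In TREF 03 and TREF 04, drop the Day 90 Yes/No cells or mark them supportive.
4. Replace the seroconversion footnote under TREF 01 and TREF 02 with the protocol definition, and state that it applies at Day 90 too: below 1:10 rising to at least 1:40, or at least 1:10 with a four-fold rise.

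The cost is wording in two synopses plus a few table and figure shells. No participants, visits or samples are added, and the sample size is unchanged.
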